#### 1.5 Patient Reported Outcomes

Patient-reported outcomes (PROs) capture unique data on treatment toxicities and disease symptoms that complements clinician-rated toxicities. In addition, it is important to understand from the patient perspective how the addition of this novel agent, entinostat, will impact overall health-related quality of life (HRQL). Collecting PROs to document treatment toxicities from the patient's perspective will provide invaluable data to inform patient-centered counseling regarding the risks and benefits of endocrine therapy plus entinostat if the combination should prove to prolong PFS or OS. This lesson has been re-capitulated in the experience with exemestane and everolimus, where concerns over increased toxicity limit the use of everolimus in the hormone-refractory setting.

Prior studies have generally indicated entinostat is well tolerated, so we expect that overall HRQL will be comparable between treatment arms. However, we

recognize the use of this novel agent in a novel treatment regimen may be associated with unanticipated side effects. We have designed the PRO endpoints for this trial to detect the most common treatment side effects and to also detect decrements to HRQL related to unanticipated side effects. We anticipate the most common side effect associated with entinostat combination will be fatigue, which is common in metastatic breast cancer due to disease. However, entinostat has also been associated with nausea, anorexia and diarrhea and these symptoms may also be more common in the exemestane and entinostat arm. Therefore, we propose to administer PRO measures to assess overall HRQL as well as specific treatment-related symptoms to detect differences between the two treatment arms.

Given that PFS is a primary endpoint for this trial, we will also evaluate whether improvement in PFS is associated with improved HRQL. To answer this question, we will assess whether the addition of entinostat to exemestane improves time to treatment deterioration (TTD) compared to exemestane + placebo. TTD is a composite endpoint consisting of time to death, disease progression, or worsening of symptoms. TTD has been used as an endpoint in a phase III study of renal cell cancer comparing two similar oral agents (axitinib vs sorafenib). As the primary endpoint, Rini et al were able to demonstrate that axitinib extended PFS compared with sorafenib (6.7 mos vs 4.7 mos,  $p < 0.0001$ ). Because of the valuable addition of TTD as an endpoint, they were also able to demonstrate that axitinib accomplished this without negatively affecting HRQL, and in fact was associated with less deterioration in HRQL (axitinib was associated with a 17% reduction in risk for TTD, HR 0.83,  $p = 0.01$ ). This is invaluable data for clinicians and patients when making treatment decisions that balance PFS benefit with possible treatment toxicities.

Because we believe that the benefits from improving PFS (and thus symptoms from disease) will outweigh any increase in toxicity from the addition of entinostat to exemestane, we hypothesize that the combination arm (EE) will have a significantly longer TTD than the EP arm.

The National Cancer Institute's Patient-Reported Outcomes version of the Common Terminology Criteria for Adverse Events (PRO-CTCAE) is a library of 78 items developed to obtain patient reporting of Adverse Events (AEs) in clinical trials. The NCI is seeking partnerships with clinical trials investigators by embedding PRO-CTCAE into therapeutic trials. The PRO-CTCAE data collected will be used to provide descriptive and parallel information about using this new measurement system to gather information directly from patients about the symptomatic adverse effects of their treatment. Content validity of PRO-CTCAE items has been established through cognitive interviews with 127 adults with different cancer types and undergoing chemotherapy or radiation therapy. Interviews and review of PRO-CTCAE items established the content validity of PRO-CTCAE items for patient-reporting of AEs. Interviews demonstrated that most AE terms were comprehended, and the attribute terms and response options required no modifications. The next step in establishing the validity of PRO-CTCAE items includes administering select items in the context of a cancer clinical trial. Given the phase III, double-blind placebo-controlled randomized design of this trial, E2112 offers the opportunity to validate PRO-CTCAE items to measure six symptoms: decreased appetite, diarrhea, nausea, vomiting, joint aches, and muscle aches. These toxicities were selected because we anticipate these to be the most common toxicities associated with entinostat or

exemestane. In addition, we anticipate that PRO-CTCAE items may identify toxicities earlier than would be identified using the clinician-rated CTCAE system. This will provide the opportunity to intervene earlier to manage symptoms that may interfere with treatment adherence.

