#### 9.3.3 Time to Treatment Deterioration (TTD)

Another secondary endpoint of the study is to evaluate time to treatment deterioration (TTD) of arm A vs. B. TTD is a composite endpoint and it captures toxicity (measured by symptom worsening), symptom worsening due to disease progression between radiological tumor assessments (provided symptoms are being assessed more frequently than the radiological disease assessments), radiological confirmed disease progression and death. TTD is defined as time

from randomization to radiological confirmed disease progression or death or worsening of symptoms, whichever occurs first. Disease progression is assessed per RECIST v1.1. Symptoms deterioration will be measured by 6 items from the 8-item FACT-Breast Symptom Index (FBSI). The 6 items (GP1, GP2, GP4, GF7, B1, P2, scored 0-24) were selected as being most clinically relative and most responsive to “proximal” change based from clinical deterioration. In addition, the other two items (GP3 or GE6) in the 8-item FBSI will be collected as well for explanatory analysis.

The selected 6 items capture both symptoms related to progressive breast cancer (fatigue, malaise, pain, shortness of breath, overall change in QOL) as well as symptoms related to entinostat (fatigue, nausea, overall change in QOL). According to Yost et al, the minimally important difference (median 2.2, range 1.5-2.5) and anchor-based criteria overlapped (PSR 2.8 and 3.2), and based on these criteria, 2-3 point changes in this 8-item FBSI survey can be interpreted as a MID. To be conservative, symptom deterioration is defined as two consecutive available decreases of at least 3 points from baseline using the 6-item FBSI in this trial, and the second visit time will be used as the time of symptom deterioration in this case, unless it is the final score, for which one decrease is sufficient.

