In order to fully capture the impact of toxicity and disease progression before radiological assessment on patient’s QOL, symptoms will be assessed every cycle for the first six months after randomization, every two cycles between 6 months and 1 year. It then will be assessed based on the same schedule for tumor assessments until disease progression. Since symptom change cannot be associated with protocol therapy if the patient never receives any treatment on protocol, the primary population for the TTD analysis will be the enrolled 360 patients for the PFS analysis who receive at least one dose of protocol therapy (i.e., all treated patients in the first 360 enrolled patients). TTD will not be evaluated on the additional 240 patients primarily enrolled for the OS endpoint.

Because we expect that the benefits from improving PFS (and thus less symptoms from disease) on arm A will outweigh any increase in toxicity from the addition of entinostat to exemestane (more symptoms from the treatment), we hypothesize that the combination arm (A) will have a significantly longer TTD than arm B. It is expected that symptom deterioration will occur before radiological confirmed disease progression or death for some patients. Hence, the median TTD should be shorter than the median PFS for the same patient population. To be conservative, we assume that the median TTD is 4 months for patients on arm B, similar with our estimate for PFS in these patients. Assuming 9 patients (9/180=5%) will not start protocol therapy in each arm, with 171 evaluable patients per arm, there is 88% power to detect a HR of 0.67 for arms A/B based on the log-rank test when the analysis is conducted 30 months after study activation (same time as the primary analysis of PFS), assuming a median TTD

of 6 months on arm A (i.e., 50% improvement in median TTD), with a 2.5% one-sided type I error rate.

Rev. Add5

9.4 Analysis Plan for Primary Endpoints, Objective Response, Toxicity and Time to Treatment Deterioration

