at diagnosis, prior adjuvant chemotherapy, prior hormonal therapy, et al. The assumption of proportionality in the Cox models will be assessed by investigating the weighted Schoenfeld residuals for each predictor. Patients with missing values for covariates will be excluded from modeling when the proportion of missingness is less than 5% and will be imputed appropriately if the proportion of missingness is  $\geq 5\%$ . ORR will be summarized along with the exact binomial 95% confidence interval and compared between the two arms using Fisher's exact tests.

TTD is defined as time from randomization to disease progression or death or worsening of symptoms, whichever occurs first. All primary analysis for TTD will be based on all cases receiving at least one dose of protocol treatment (i.e., all treated population). The distribution of TTD will be estimated using Kaplan-Meier method, and TTD comparisons between treatment arms will be tested primarily using log-rank test. Cox proportional-hazards models will be conducted to estimate the HR for treatment effect for TTD as a supportive analysis. Same factors included in the multivariable Cox model for PFS and baseline symptom level will be included as predictors for TTD.

Analyses pertaining to toxicity will be based on all treated cases. Adverse events will be graded using the National Cancer Institute (NCI) Common Terminology Criteria for Adverse Events (CTCAE). All treatment-emergent and baseline adverse events and hematological/biochemical toxicities based on laboratory measurements, as well as drug related AE's, will be summarized by treatment group and NCI CTCAE worst grade. The incidence of deaths and treatment-emergent serious adverse events (defined as number of patients experiencing the AE divided by all treated patients) will be summarized and compared between treatment arms using Fisher's exact test. Also, the incidence of adverse events leading to discontinuation of investigational product and/or withdrawal from the study will be summarized and listed.

In all analyses, P-values will be two-sided. A level of 0.2% will be considered statistically significant for stratified log rank test for the primary PFS analysis. For OS comparison, the significance level for stratified log rank test will be 4.8%. For all other tests, a level of 5% will be considered statistically significant.

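### Section 1.5 uses TTD to judge whether a PFS gain comes with better HRQL, but a significant TTD can arise from the PFS effect alone and does not by itself show preserved or improved HRQL

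*Combined protocol and SAP*

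**What the plan says.** Section 1.5 sets the question: "we will also evaluate whether improvement in PFS is associated with improved HRQL". It then gives the means of answering it: "To answer this question, we will assess whether the addition of entinostat to exemestane improves time to treatment deterioration (TTD"). The same section defines the endpoint: "TTD is a composite endpoint consisting of time to death, disease progression, or worsening of symptoms". It cites a renal cell trial in which a TTD hazard ratio of 0.83 was read as PFS gained without harm to HRQL and with less HRQL deterioration.

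Section 9.3.3 measures TTD "from randomization to radiological confirmed disease progression or death or worsening of symptoms, whichever occurs first". For the symptom part, "symptom deterioration is defined as two consecutive available decreases of at least 3 points from baseline using the 6-item FBSI", with a single decrease sufficient if it is the final score. The section expects that the PFS benefit "will outweigh any increase in toxicity from the addition of entinostat to exemestane" and so hypothesises a longer TTD on arm A.

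In Section 9.4, "TTD comparisons between treatment arms will be tested primarily using log-rank test", with Kaplan-Meier curves and Cox models on the same composite. Neither section plans a breakdown of first events, a symptom-only analysis or a competing-risk analysis. Section 5.6.3.1 collects no FBSI at or after progression.

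HRQL is also tested separately in Section 9.6, using the Trial Outcome Index and four entinostat-related symptoms.

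**The concern.** Progression and death make up nearly all of PFS, and both also count in TTD. If entinostat delays progression, TTD lengthens for that reason, whatever happens to symptoms. Using TTD to say what a PFS gain does to HRQL is therefore partly circular. With only the composite analysed, the report could not tell a TTD gain that includes symptoms from one due wholly to delayed progression.

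At stake is the claim that Section 1.5 wants for clinicians and patients: longer PFS without loss of HRQL. Followed as written, that claim could be made while confirmed symptom deterioration occurs at a higher rate on entinostat.

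**Working it through.** **Inputs from the plan.** PFS median 4.1 months on arm B and PFS hazard ratio 0.58 (Section 9.2.1). TTD medians 4 and 6 months, hazard ratio 0.67, 171 patients per arm, one-sided 2.5% (Section 9.3.3). Accrual over 24 months, with data cut at month 24 and then 6 months of cleaning (Section 9.2.1).

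**Reproducing the plan's power.** With exponential times, uniform accrual over T = 24 months and no further follow-up, expected events per arm are n × [1 − (1 − exp(−hT))/(hT)].
- TTD hazards: ln 2/4 = 0.1733 and ln 2/6 = 0.1155 per month.
- TTD events: 130.5 + 113.2 = 243.7.
- Power: Φ(|ln 0.67| × √243.7/2 − 1.96) = 87.8%, against 88% stated.
- The same model with 180 per arm gives 247.2 PFS events, against 247 stated.

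**Model for the composite.** TTD hazard = PFS hazard + symptom-first hazard, taken as independent.
- PFS hazards: ln 2/4.1 = 0.1691 on B and 0.58 × 0.1691 = 0.0981 on A.
- Symptom hazards: s on B and k × s on A.
- The plan does not give s. I assume 0.02 to 0.06 per month. The symptom share of arm B TTD events is s/(0.1691 + s), which is 10.6%, 19.1% and 26.2% at s = 0.02, 0.04 and 0.06.

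**Worked case, s = 0.04 and k = 1.5.**
- B: 0.1691 + 0.04 = 0.2091. A: 0.0981 + 0.06 = 0.1581. TTD hazard ratio 0.756.
- Events: 137.1 + 126.9 = 264.
- Power: Φ(0.280 × √264/2 − 1.96) = 62%.

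**Grid: TTD hazard ratio and probability of significance.**

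| s per month (share on B) | k = 1 | k = 1.25 | k = 1.5 | k = 2 |
|---|---|---|---|---|
| 0.02 (11%) | 0.62, 96% | 0.65, 92% | 0.68, 87% | 0.73, 71% |
| 0.04 (19%) | 0.66, 92% | 0.71, 80% | 0.76, 62% | 0.85, 26% |
| 0.06 (26%) | 0.69, 86% | 0.76, 64% | 0.82, 37% | 0.95, 6% |

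**Sensitivity.**
- PFS hazard ratio 0.73 (the phase 2 value in Table 1.1) with s = 0.02: 60% at k = 1 and 39% at k = 1.5.
- Symptom share of 30% at the design PFS effect: 25% at k = 1.5 and 2% at k = 2.
- A simulation with 12-weekly progression visits and 4-weekly symptom visits (500 runs per scenario) gave somewhat lower figures. At a 20% share it gave 64%, 47% and 12% for k = 1.25, 1.5 and 2, against 78%, 59% and 22% from the formula.

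**Which component measure to use.** Take equal symptom hazards and s = 0.04. Long-run cumulative incidence of symptom-first deterioration is 0.04/0.1381 = 29% on A and 0.04/0.2091 = 19% on B. Expected symptom-first counts at the cut are 35 and 26. Both are higher on A only because patients stay progression-free longer. The cause-specific hazard ratio in this case is 1.

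**Information in the component.** Symptom-first events in both arms total about 33 to 85 with equal hazards and 42 to 101 at k = 1.5. An approximate 95% interval for the hazard ratio multiplies and divides the estimate by exp(1.96 × 2/√d), which is 1.98 at d = 33 and 1.53 at d = 85.

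**The case against.** TTD is openly a net-benefit composite. Section 9.3.3 says that it combines toxicity, symptoms, progression and death, and enough symptom harm can defeat it: the grid falls to 6%. Sections 9.3.3 and 9.4 contain no rule that equates a positive TTD with preserved HRQL. HRQL and entinostat symptoms are separate secondary objectives (2.2.5 and 2.2.6), with their own error rate and power in Section 9.6 and an alternative that arm A is worse.

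Most of this stands, and it rules out several stronger readings.
- A reader might infer that TTD is likely to succeed whatever happens to symptoms. The documents do not support that, because the symptom-first share is not given and the result needs the design PFS effect.
- A reader might take the 4-month control TTD beside the 4.1-month PFS as proof that progression dominates, or derive from the four medians a symptom hazard about four times higher on A (0.0175 against 0.0042 per month). The plan labels the 4 months conservative and says that TTD should be shorter than PFS. It is a power assumption, and the ratio rests on a rounding-size difference of 0.1 month.
- A reader might infer that HRQL harm goes otherwise untested, or is tested at one time point on unrelated scales. Section 9.6.2 compares arms at several time points and fits mixed models, and the Trial Outcome Index shares GP2, GP4 and GF7 with the six FBSI items.

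What does not answer the point is that none of the Section 9.6 analyses shows what drove a positive TTD, and Section 1.5 names TTD, not those analyses, as the answer to its question.

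**Conclusion.** The concern holds in a limited form. The fault lies in the inference that Section 1.5 draws from TTD; the TTD test itself is sound. At the design PFS effect and an assumed 11 to 26% symptom share, TTD is significant 86 to 96% of the time when entinostat does nothing to the symptom hazard. It is still significant 37 to 87% of the time when that hazard is 1.5 times higher. So a positive TTD cannot carry an HRQL conclusion alone.

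These figures rest on exponential times, independence of symptoms and progression, a PFS hazard ratio of 0.58 and a symptom rate that the plan does not state. With a doubled hazard, a share near 30% or a PFS hazard ratio of 0.73, the chance is much lower. That the meaning of a positive TTD depends on an unreported event mix is itself a reason to report the mix. TTD is a secondary endpoint, but Section 5.6.3 calls it critical and Section 1.5 intends it to inform treatment decisions.

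**What to change.** Keep the TTD log-rank test. In Sections 9.3.3 and 9.4, prespecify:
- first-event type (symptom deterioration, progression, death) by arm;
- as the lead component measure, the cause-specific hazard ratio with 95% confidence interval for confirmed 6-item FBSI deterioration, censoring at progression or death;
- cumulative incidence as description only, since delayed progression raises it on entinostat even when symptom hazards are equal. For the same reason, neither it nor raw first-event counts should decide whether an HRQL claim is allowed.

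Reword Section 1.5 so that TTD is reported as a net-benefit composite. Any HRQL statement should rest on the symptom-component estimate together with the Section 9.6 HRQL and symptom comparisons.

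The cost is SAP wording and a small analysis of data already collected, with no alpha, sample size or visits affected. The downside is few component events, hence a wide interval and an HRQL claim that is harder to make.

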## 2. Objectives

### 2.1 Primary Objective

- 2.1.1 To evaluate whether the addition of entinostat to endocrine therapy (exemestane) improves progression-free survival (PFS) and/or overall survival (OS) in patients with HR-positive, HER2-negative locally advanced or metastatic breast cancer who have previously progressed on a non-steroidal aromatase inhibitor (AI).

Rev.10/15

### 2.2 Secondary Objectives

- 2.2.1 To evaluate the safety and tolerability of entinostat in combination with exemestane, and to compare the safety profile to that of endocrine therapy with placebo.
- 2.2.2 To evaluate the objective response rate of exemestane in combination with entinostat or placebo.
- 2.2.3 To evaluate whether the efficacy of exemestane with entinostat varies with changes in acetylation status in peripheral blood mononuclear cells (PBMCs).
- 2.2.4 To evaluate the time to treatment deterioration (as defined by decrease in HRQL, progression, death) of exemestane + entinostat versus exemestane + placebo arms.
- 2.2.5 To evaluate the differences in overall health-related quality of life (HRQL) between the exemestane + entinostat versus exemestane + placebo arms.
- 2.2.6 To evaluate the difference with respect to specific symptoms that are associated with entinostat, i.e., fatigue, nausea, anorexia and diarrhea, between the exemestane + entinostat versus exemestane + placebo arms.
- 2.2.7 To measure adherence to protocol therapy.
- 2.2.8 To evaluate the pharmacokinetics of entinostat in patients with advanced breast cancer.
- 2.2.9 To evaluate what, if any, patient variables alter the pharmacokinetic profile of entinostat in patients with advanced breast cancer.

Rev.10/16

### 2.3 Exploratory Objectives

- 2.3.1 To collect archival tumor samples and germline DNA to explore other potential biomarkers of therapeutic efficacy.
- 2.3.2 To collect patient ratings of AEs using select PRO-CTCAE items to evaluate the psychometric properties of PRO-CTCAE items and explore the incorporation of PRO-CTCAE items into a phase III double-blind placebo-controlled trial.

### 3. Selection of Patients

Each of the criteria in the checklist that follows must be met in order for a patient to be considered eligible for this study. Use the checklist to confirm a patient's eligibility. For each patient, this checklist must be photocopied, completed and maintained in the patient's chart.

**In calculating days of tests and measurements, the day a test or measurement is done is considered Day 0. Therefore, if a test is done on a Monday, the Monday four weeks later would be considered Day 28.**

ECOG-ACRIN Patient No. \_\_\_\_\_

Patient's Initials (L, F, M) \_\_\_\_\_

**NOTE:** All questions regarding eligibility should be directed to the study chair or study chair liaison.

**NOTE:** Institutions may use the eligibility checklist as source documentation if it has been reviewed, signed, and dated prior to randomization by the treating physician.

#### 3.1 Eligibility Criteria

\_\_\_\_\_ 3.1.1 Estrogen receptor (ER) and/or progesterone receptor (PR) positive histologically confirmed adenocarcinoma of the breast with staining of  $\geq 1\%$  cells will be considered positive. Receptor status may be based on any time during treatment prior to study randomization, and from any site (i.e. primary, recurrent, or metastatic).

\_\_\_\_\_ 3.1.2 Patients whose tumors have HER2 IHC 3+, ISH  $\geq 2.0$ , or average HER2 copy number  $\geq 6.0$  signals per cell are not eligible. Receptor status may be based on any time during treatment prior to study randomization, and from any site (i.e. primary, recurrent, or metastatic).

\_\_\_\_\_ 3.1.3 Patients must have measurable or non-measurable Stage III/locally advanced or metastatic carcinoma of the breast, as defined in Section [6.1.2](#), where local therapy with curative intent is not possible. Lesions must be evaluated  $\leq 4$  weeks prior to study randomization. Diagnostic-quality CT scans with both oral and IV contrast are the expected radiologic method, unless an alternative is approved per Section [6.1.3](#).

**NOTE:** Where baseline imaging has already been performed  $\leq 6$  weeks prior to study randomization, repeat imaging may not be required. Please refer to footnotes 5 and 6 of Study Calendar (Section [7](#)).

**NOTE:** As of October 16, 2016, accrual of new patients having non-measurable disease has stopped. Per Section [9.2](#), the planned accrual for this target population has been reached.

Rev. Add5

Rev.10/15

- \_\_\_\_\_ 3.1.4 Pre/peri- and postmenopausal women and all men are eligible for this trial. Postmenopausal is defined as:
- Age  $\geq$  55 years and one year or more of amenorrhea.
  - Age  $<$  55 years and one year or more of amenorrhea, with estradiol  $<$  20 pg/ml.
  - Age  $<$  55 with prior hysterectomy but intact ovaries, with estradiol  $<$  20 pg/ml.
  - Prior bilateral oophorectomy.

**NOTE:** Women who do not fit the criteria for being postmenopausal as above are deemed pre- or peri-menopausal. Pre/perimenopausal women and all men can enroll provided they agree to receive concomitant LHRH agonist. Pre/perimenopausal women must have commenced treatment with LHRH agonist at least 4 weeks prior to randomization. If patients have received alternative LHRH agonist prior to study entry, they must switch to goserelin for the duration of the trial.

Rev.10/15

- \_\_\_\_\_ 3.1.5 Sexually active males and pre/perimenopausal women must agree to use an accepted and effective method of contraception or to abstain from sexual intercourse for the duration of their participation in the study and for 3 months after discontinuation of therapy.

Rev.10/15

- \_\_\_\_\_ 3.1.6 Women must not be pregnant or breast-feeding.
- All females of childbearing potential must have a blood test or urine study  $\leq$  2 weeks prior to randomization.
- A female of childbearing potential is any woman, regardless of sexual orientation or whether they have undergone tubal ligation, who meets the following criteria: 1) has not undergone a hysterectomy or bilateral oophorectomy; or 2) has not been naturally postmenopausal for at least 24 consecutive months (i.e., has had menses at any time in the preceding 24 consecutive months).

Female? \_\_\_\_\_ (Yes or No)

Date of blood test or urine study: \_\_\_\_\_

- \_\_\_\_\_ 3.1.7 Patients must not have known central nervous system metastasis or a history of CNS metastases. Patients with leptomeningeal disease are not eligible.

- \_\_\_\_\_ 3.1.8 Patients must be disease-free of prior invasive malignancies for  $>$  5 years with the exception of curatively-treated basal cell or squamous cell carcinoma of the skin or carcinoma in situ of the cervix.

**NOTE:** If there is a history of prior malignancy, patients must not be receiving other specific treatment for that cancer.

Rev. 4/15

- \_\_\_\_\_ 3.1.9 Patients must meet at least one of the following criteria:
- \_\_\_\_\_ 3.1.9.1 Disease progression any time after non-steroidal AI use in the advanced disease setting.

Rev. 10/15  
Rev. 10/16

3.1.9.2 Relapse while on or within  $\leq 12$  months of end of adjuvant non-steroidal AI therapy with or without prior endocrine therapy for advanced disease.

**NOTE:** In either setting, treatment with any prior endocrine therapy must be completed  $\geq 2$  weeks prior to C1D1 of study treatment with the exception of exemestane which is permitted in the advanced disease setting within  $\leq 4$  weeks immediately prior to C1D1. Prior adjuvant exemestane is allowed if the disease free interval is  $>12$  months from the discontinuation of exemestane. Prior faslodex, everolimus, palbociclib or other CDK inhibitor (e.g. ribociclib, abemaciclib) use are allowed and must have been completed  $\geq 2$  weeks prior to C1D1. Failure to adhere to this washout guideline will result in a protocol violation.

Rev. 10/16

\_\_\_\_\_ 3.1.10 Patients may have received only one prior chemotherapy regimen for metastatic disease provided treatment was completed  $\geq 3$  weeks prior to randomization.

\_\_\_\_\_ 3.1.11 Patients may be treated with bone modifying agents such as bisphosphonates or RANK-ligand agents (e.g. denosumab) per ASCO guidelines. Whenever possible, patients requiring bone modifying agents should start treatment  $\geq 7$  days prior to study therapy and should continue the same agent throughout study unless clinically compelled to change.

\_\_\_\_\_ 3.1.12 Prior radiotherapy must in general have been completed  $\geq 2$  weeks prior to randomization and patients must have recovered from the toxicity of the radiation.

**NOTE:** Patients may receive concurrent radiation therapy to painful sites of bony disease or areas of impending fracture as long as sites of measurable or non-measurable disease outside the radiation therapy port are available to follow.

\_\_\_\_\_ 3.1.13 Patients must NOT receive concurrent anti-cancer therapy or investigational agent unless specified in protocol.

Rev. 10/16

\_\_\_\_\_ 3.1.14 Patients must NOT be receiving valproic acid, an HDAC inhibitor, and may not have previously received any HDAC inhibitor prior to enrollment (e.g valproic acid, entinostat, vorinostat) unless discussed with the study chair. Patients must not have received prior HDAC therapy for the treatment of their malignancy.

Rev. 10/16

\_\_\_\_\_ 3.1.15 Patients must have no known allergies to exemestane, entinostat, or medications that have a benzamide structure (e.g., tiapride, remoxipride, clebopride).

\_\_\_\_\_ 3.1.16 Patients must NOT suffer from medical or psychiatric conditions that would interfere with protocol compliance, the ability to provide informed consent, or assessment of response or anticipated toxicities. This includes uncontrolled intercurrent illness including, but not limited to ongoing or active infection.

- 
- \_\_\_\_\_ 3.1.17 Patients must have recovered from all clinically relevant adverse events to grade 1 or baseline due to previous agents administered (except alopecia) and the criteria outlined in Section [3.1.18](#).
- \_\_\_\_\_ 3.1.18 Patients must have adequate hematologic, liver and renal function as defined below  $\leq 28$  days prior to randomization:
- \_\_\_\_\_ 3.1.18.1 Hemoglobin (Hgb)  $\geq 9.0$  g/dL  
Hemoglobin: \_\_\_\_\_  
Date of Test: \_\_\_\_\_
- \_\_\_\_\_ 3.1.18.2 Platelet count  $\geq 100,000/$  mL  
Platelets: \_\_\_\_\_  
Date of Test: \_\_\_\_\_
- \_\_\_\_\_ 3.1.18.3 Absolute neutrophil count  $\geq 1,500/$ mL  
Neutrophil count: \_\_\_\_\_  
Date of Test: \_\_\_\_\_
- \_\_\_\_\_ 3.1.18.4 Creatinine  $\leq 2.0$  mg/dL  
Creatinine: \_\_\_\_\_  
Date of Test: \_\_\_\_\_
- \_\_\_\_\_ 3.1.18.5 Total bilirubin  $< 1.5 \times$  institutional upper limit of normal ( $\leq 3$  mg/dL in case of Gilbert's syndrome)  
Total bilirubin: \_\_\_\_\_ ULN: \_\_\_\_\_  
Date of Test: \_\_\_\_\_
- \_\_\_\_\_ 3.1.18.6 Transaminases (ALT, AST)  $\leq 2.5 \times$  institutional upper limit normal  
ALT: \_\_\_\_\_ ULN: \_\_\_\_\_  
Date of Test: \_\_\_\_\_  
AST: \_\_\_\_\_ ULN: \_\_\_\_\_  
Date of Test: \_\_\_\_\_
- NOTE:** It is preferred that laboratory values for eligibility be assessed after the last dose of prior treatment, especially in cases where most-recent treatment prior to study entry is chemotherapy.
- \_\_\_\_\_ 3.1.19 Known HIV-positive patients should have a CD4 count  $> 250/mm^3$ .
- \_\_\_\_\_ 3.1.20 Patients must have ECOG Performance Status 0-1. See [Appendix V](#).
- \_\_\_\_\_ 3.1.21 Patients must have a life expectancy  $\geq 12$  weeks.
- \_\_\_\_\_ 3.1.22 Patients must be  $\geq 18$  years of age.

\_\_\_\_\_ 3.1.23 Patients must be able to swallow tablets.

\_\_\_\_\_  
Physician Signature

\_\_\_\_\_  
Date

**OPTIONAL:** This signature line is provided for use by institutions wishing to use the eligibility checklist as source documentation.

Rev.7/14  
Rev. Add5

